ClinicalTrials.gov ID: NCT04662801

Title: Weight Regain Treatment Post-Bariatric Surgery

Date: 11/30/2021

Document: Protocol w SAP

CLINICAL STUDY PROTOCOL

A Behavioral Treatment with Sequenced Adjunctive Pharmacotherapy for Weight Regain After Bariatric Surgery: A Pilot Study

Protocol Number

2000029491

Principal Investigator

[name]

Sponsor

American Psychological Foundation

Protocol Version

November 16, 2021

Confidentiality Statement:

Study Personnel

Principal Investigator

[name]
Email: [contact]

Investigator

[name]
Email: [contact]

Medical Monitor

[name]
Email: [contact]

Key Study Personnel:

[name]
Email: [contact]

Synopsis

Primary Objective

This study aims to evaluate the feasibility and acceptability of adding a specific pharmacological treatment (Naltrexone+Bupropion combination [NB]) to behavioral treatment for non-responders among adults experiencing weight regain following metabolic and bariatric surgery (MBS). A behavioral treatment will be given to all subjects as the primary treatment. After one month of behavioral treatment, patients who do not show a "response" (based on weight-loss data) will begin a trial of a specific medication (in addition to continuing the behavioral therapy); repeated multi-modal assessments will assess whether the combined approach augments the behavioral therapy.

We hypothesize that the treatments will be feasible and acceptable to subjects, and that subjects will experience significant weight loss and improvements in psychosocial functioning. More specifically, it is hypothesized that early responders to BWL will show weight loss during the trial, while the addition of NB will aid early non-responders in achieving weight loss.

Secondary Objectives (if applicable)

This pilot will also examine whether augmenting behavioral treatment with NB results in improvements in psychosocial functioning.

Study Duration

Study duration will be three months.

Study Design

The proposed clinical trial will pilot the feasibility and acceptability of delivering behavioral weight loss treatment (BWL) to adults struggling with weight regain after MBS. All participants will receive BWL treatment. Early weight loss responders will continue with BWL for the duration of treatment, while early non-responders will be given NB as an adjunct to BWL. The pilot will also examine whether augmenting behavioral treatment with NB results in weight loss and improvements in psychosocial functioning.

Study Population

N=25 adults (aged 18-65) who experience weight regain after MBS will participate in the study. Weight regain will be defined by the recommended definition of weight regain in the field, that is, weight regain defined as the percentage of maximum weight lost ($[100 * (\text{post-nadir weight} - \text{nadir weight})] / (\text{pre-surgery weight} - \text{nadir weight})$). Weight regain based on this definition was the best indicator of poor clinical outcomes.

Number of Participants

N=25

Number of Study Sites 1
Primary Outcome Variables Primary outcomes will include: 1) feasibility, 2) acceptability, and 3) weight loss. 1) Feasibility will be determined by examining enrollment, number of sessions attended, compliance, and retention. 2) Treatment credibility and satisfaction will be examined via self-report. 3) To examine weight changes, we will examine percent total weight loss for the entire participant group. We will also compare percent weight loss for the two responder groups.
Secondary and Exploratory Outcome Variables (if applicable) Secondary outcomes include changes in psychosocial functioning including eating-disorder psychopathology, depressive symptoms, and food cravings.

Abbreviations

Abbreviation	Explanation
NB	Naltrexone+Bupropion
MBS	Metabolic and Bariatric Surgery
RYGB	Roux-en-Y gastric bypass
LSG	Sleeve gastrectomy
BMI	Body Mass Index
BWL	Behavioral Weight Loss

Table of Contents

Synopsis.....
Primary Objective
Secondary Objectives (if applicable)
Study Duration
Study Design
Study Population.....
Number of Participants
Number of Study Sites
Primary Outcome Variables.....
Secondary and Exploratory Outcome Variables (if applicable)
Visit Schedule Table (Optional)
Study Flow Chart (optional)
Abbreviations
Glossary of Terms.....
1 - Introduction

1.1 Introductory Statement

Metabolic and bariatric surgery (MBS) is the most effective treatment for severe obesity and associated sequelae. Despite MBS' overall efficacy, weight regain with recurrence and/or onset of medical and psychological comorbidities is common and a matter of great concern. Very little is known about post-MBS treatments for weight regain. The goals of this proposal are to evaluate the feasibility and acceptability of evidence-based obesity treatments in post-MBS patients. All eligible subjects who experience weight regain after MBS will be given behavioral treatment (BWL). After one month of BWL treatment, "treatment response" will be determined based on early weight loss status because of its strong prognostic significance for optimal weight loss outcomes. Early weight-loss responders will continue BWL treatment, while *non*-responders will be given a pharmacologic agent to augment BWL treatment. This study aims to explore whether the addition of specific pharmacotherapy to BWL amongst initial non-responders improves outcomes. The study will compare the two treatment conditions and will examine within-group weight and psychosocial changes over time in the combined treatment condition; these data will serve as pilot data and represent effect-size estimates to design and power larger definitive treatment trials testing combined behavioral and pharmacological interventions and stepped-care approaches to prevent weight regain after MBS.

2 - Background

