Pharmacologic Treatment. Another promising, yet understudied, avenue involves the use of weight-loss medications after MBS. Emerging research suggests utility in weight-loss medications after MBS (13). The combination of Naltrexone and Bupropion (**NB**), also known as "Contrave," is an optimal starting point due to its consistent weight-loss evidence base, affordable costs, tolerable side-effects, safety profile, and putative mechanisms of action. In 2014, the FDA approved NB for obesity following empirical support from several RCTs performed with obesity (14). These RCTs reported significant clinically-meaningful weight losses with naltrexone plus sustained-release bupropion combined in fixed-dose pills. These

findings supporting NB medication are consistent with large RCTs which reported greater weight loss with NB than placebo (-6.5 vs -1.2% (14)). Although the name brand (Contrave) is expensive, the combination of Naltrexone and Bupropion are available at affordable prices. Putative mechanisms of action for NB seem relevant for post-MBS patients who might also be struggling with maladaptive eating behaviors, such as loss-of-control (LOC) eating. LOC eating and related eating-disorder psychopathology are consistent predictors of poor outcomes after MBS (15). As reviewed in the preliminary data section below, NB may be helpful in both reducing problematic eating such as LOC eating (i.e., binge eating) and weight loss. Putative mechanisms of action for NB is especially relevant for reducing LOC eating and weight per hypothesized effects on brain regions implicated in the regulation of food intake and weight based on the mechanisms of action of leptin (16).

Early Weight Loss. Meaningful early weight loss, ranging from 0.5 to 3% weight loss during the first 1-2 months of treatment, is a consistent predictor of weight loss by the end of treatment and longer-term (17). Earlier work has found that at least 1% weight loss early in treatment was associated with meaningful weight loss at the end of treatment (17).

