Collectively, the lack of evidence-based treatments after MBS remains a critical and concerning gap in the field. An evidence base is urgently needed to direct the field in managing obesity after surgical intervention. Given that BWL and NB are both empirically-based weight-loss treatments, the proposed study will pilot the feasibility and acceptability of delivering behavioral treatment (BWL) to adults struggling with weight regain after MBS. Early weight loss responders will continue with BWL for the duration of treatment, while early non-responders will be given NB as an adjunct to BWL. The pilot will also examine whether augmenting behavioral treatment with NB results in weight loss and improvements in psychosocial functioning. These data will inform designs and provide effect size data to power larger definitive trials examining stepped care approaches with behavioral and pharmacological interventions for post-MBS.

3 - Rationale/Significance

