5.3.1 Number of Participants

N=25 adults who underwent MBS at the Yale bariatric surgery center will be recruited to participate in the study.

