6.1.3 Method of Assignment/Randomization (if applicable)

NA

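### The pilot's effect sizes are meant to power definitive trials, but non-randomized groups formed by Month-1 weight loss, with N=25, cannot supply a usable planning effect

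*Combined protocol and SAP*

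**What the plan says.** Section 1.1 (Introductory Statement) says the study will compare the two treatment conditions and examine within-group change in the combined condition, and that these data will "represent effect-size estimates to design and power larger definitive treatment trials". Section 3.2 repeats the statement. Section 2.1 puts it as "These data will inform designs and provide effect size data to power larger definitive trials". Section 7.18 adds that the data will serve as pilot data for definitive RCTs.

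On size, section 5.3.1 gives "N=25 adults who underwent MBS at the Yale bariatric surgery center". No effect size, SD, alpha, power or precision target supports that number. The contents list a section 6.4.2 on sample size, but the body goes from 6.4.1 to section 7.

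On assignment, section 6.1.3 reads NA. Sections 1.1 and 6.3 form the groups by weight-loss response after one month of BWL: responders continue BWL and non-responders have NB added. Neither the expected split nor a study definition of response is given; section 2.1 only describes earlier work, "Meaningful early weight loss, ranging from 0.5 to 3% weight loss during the first 1-2 months of treatment", and mentions a loss of at least 1%.

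On analysis, section 6.4.1 plans a mixed model with treatment, time and their interaction, and a 95% CI for percent weight loss in the non-responder arm.

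**The concern.** Two effect sizes could be carried forward: the contrast between BWL and BWL+NB, and the within-arm change on BWL+NB. A planning effect has to estimate the quantity that the next trial will test, and be precise enough to bound a sample size. Both estimates fail the first requirement because of how the groups are formed, and at N=25 both are weak on the second. A definitive trial sized on either could be badly too small or too large. The between-group figure might even point the wrong way, since selection favors the group that does not receive NB.

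**Working it through.** The plan's own figure, N=25, cannot be reproduced because it comes with no inputs. The checks below work in SD units. Every split, correlation and observed effect is an assumption, since the documents give none.

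**1. What the between-group d measures when NB does nothing.** Let Month-1 and Month-3 loss be jointly normal with correlation r, and let a proportion p fall below the response cut. With z the p-quantile of the standard normal and φ its density:

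d = [rφ(z) / (p(1-p))] / √[1 - r²φ(z)² / (p(1-p))]

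Take p = 14/25 = 0.56, so z = 0.151, φ = 0.3944 and p(1-p) = 0.2464:

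| r | mean difference | within-group SD | d favoring responders |
|---|---|---|---|
| 0.3 | 0.480 | 0.971 | 0.49 |
| 0.5 | 0.800 | 0.918 | 0.87 |
| 0.7 | 1.121 | 0.831 | 1.35 |

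A simulation of one million normal pairs gave the same three values of d. A positive r is expected: percent total weight loss is measured from pre-treatment weight (section 6.2), so Month-3 loss contains Month-1 loss. If monthly losses were independent and equally variable, r would be 1/√3 = 0.58. This bias does not shrink as N grows.

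**2. What the within-arm change measures.** Non-responders are chosen for a poor first month. Their later change combines NB, two more months of BWL and regression toward their usual rate of loss. No randomized comparison separates these.

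**3. Precision of the between-group d.** Exact 95% CIs come from inverting the noncentral t, with t = d√(n1n2/(n1+n2)) and n1+n2-2 df. For an observed d = 0.5:

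| Assumed split | 95% CI |
|---|---|
| 12 v 13 | -0.30 to 1.29 |
| 11 v 14 | -0.31 to 1.30 |
| 8 v 17 | -0.36 to 1.35 |
| 5 v 20 | -0.50 to 1.49 |

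**4. Precision of the within-arm standardized change.** With t = d√n and n-1 df, an observed 0.5 at n = 14 gives -0.07 to 1.05.

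**5. Effect on a future sample size.** For two-sided alpha 0.05 and 80% power, n per arm = 2((1.96 + 0.8416)/d)²:

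- d = 0.2: 392.4, so 393
- d = 0.5: 62.8, so 63
- d = 1.3: 9.3, so 10

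Where the lower confidence limit is at or below zero, the required n has no upper bound.

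**6. Precision of the alternative inputs.** For an SD pooled over both groups (23 df), the chi-square 95% limits are √(23/38.08) = 0.78 and √(23/11.69) = 1.40 times the estimate. Required n scales with the squared SD, so it moves by a factor of 0.60 to 1.97. Clopper-Pearson intervals for illustrative counts are: response 11/25 (44%), 24% to 65%; retention 20/25 (80%), 59% to 93%; retention 15/25 (60%), 39% to 79%.

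**The case against.** The strongest reply is that this is a pilot whose lead aims are feasibility and acceptability. No participant, procedure or planned analysis depends on the sentence about powering later trials. The suggested replacements are also imprecise, as step 6 shows, and retention and compliance are already primary feasibility outcomes. All of that is true. It limits how much weight the point carries, but it does not make the stated purpose achievable.

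Several stronger readings are tempting and should not be adopted:

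- A reader might infer that any effect size from this study will be compatible with harm, no effect and a very large benefit. That is not general. An observed between-group d of 0.9 at 11 v 14 gives 0.06 to 1.72, and a within-arm 0.8 at n = 14 gives 0.18 to 1.39. Both are wide, but both exclude zero.
- A reader might infer that imprecision is the whole problem and a larger pilot of the same design would solve it. Steps 1 and 2 show otherwise.
- A reader might infer that the sponsor will take the point estimate as the planning value and ignore its interval. The documents do not say so; section 2.1 also speaks of informing designs.
- A reader might treat 11 v 14 as the plan's split, or cut it by the highest attrition quoted. No split is stated. In section 7.12 the 30% to 45% range is for NB obesity studies, and only the 20% to 38% range is described as having comparable time frames. The planned mixed model can also use partial data, so completer counts would overstate the loss.

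**Conclusion.** The point holds. Sections 1.1, 2.1 and 3.2 assign the data a use that the design cannot support. The main reason is structural: the between-group contrast is not an NB effect at any N, and the within-arm change is not NB alone. Imprecision is the second reason. For an observed d of 0.5, the interval runs from about -0.3 to 1.3 at near-even splits and widens to -0.50 to 1.49 at 5 v 20.

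The selection bias of 0.49 to 1.35 rests on bivariate normality, correlations of 0.3 to 0.7 and a 14-of-25 non-response rate. Its size depends on those assumptions, but its direction needs only a positive correlation. The imprecision holds at every split tried.

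**What to change.** In sections 1.1, 2.1 and 3.2, replace the effect-size purpose with the following:

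- The pilot supplies the SD of percent weight change (pooled across groups where appropriate), the Month-1 response fraction, NB uptake, compliance and retention, each with a 95% CI. Uncertainty in the SD will be allowed for in planning. How to do that, for example by an upper confidence limit, can be left to the team.
- The definitive trial will be powered on a pre-stated clinically important difference justified outside this pilot.
- Between-group and within-arm effect sizes are reported descriptively with 95% CIs and are not used as the planning value. One sentence should give the reason: groups are non-randomized and formed by an early value of the outcome.

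The response fraction can be carried forward only if the definition of response used is reported with it.

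The cost is wording in three sections, with no new data or procedures. The downside is a more modest stated purpose, and the replacement inputs are themselves imprecise at n = 25.

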2.1 Background/prevalence of research topic

Individuals with obesity suffer from increased risk of cardiovascular morbidity and mortality, as well as type 2 diabetes, obstructive sleep apnea, dyslipidemias, asthma, and several cancers (1). Rates of obesity (defined as body mass index (BMI) ≥ 30) have steadily increased over the last few decades to a staggering 39.8% (2). Alarmingly, obesity prevalence in the general adult population is expected to rise to over 51%, with a 130% increase in severe obesity (BMI ≥ 40) by 2030 (3). These rates and projected future increases are deeply concerning given the substantial disease and economic burden of obesity (4). As severe obesity rates continue to rapidly rise, MBS is expected to increase. MBS is the most effective and enduring treatment for severe obesity and results in impressive acute and long-term weight loss and improvement and/or remission of medical comorbidities (5) and psychosocial sequelae (6). Currently, laparoscopic Roux-en-Y gastric bypass (RYGB) and sleeve gastrectomy (LSG) are the most commonly performed MBS procedures (7).

Despite these impressive data, weight trajectories following both forms of MBS have significant variability. Data from the NIH-funded Longitudinal Assessment of Bariatric Surgery (LABS) consortium found substantial average weight loss by 3 and 7 years post-RYGB, with most of the weight loss occurring during the first year post-surgery (8). Nonetheless, weight outcomes have marked heterogeneity in both RYGB and LSG. Lowest maximal weight loss was as low as -1.1% for LSG and -4.1% for RYGB, with ranges of 1.1-58.3% for LSG and 4.1-60.9% for RYGB (9). Even for those with optimal outcomes, weight regain is not uncommon and there exists marked variability in weight losses achieved after MBS (9). Additionally, worsening or recurrence of medical and psychological comorbidities, is of great concern (10).

Post-MBS Treatment is Needed.

Behavioral Treatment. Although the field recognizes the need for post-operative behavioral or psychosocial allied treatments, there is little guidance as to what should be provided based on empirical data. Of the limited research to date which has examined pre- and post-MBS interventions to improve weight outcomes, results suggest that pre-surgical interventions have largely been ineffective at producing significant weight differences post-surgically (11); however, behavioral treatments may have utility post-surgery (12).

Pharmacologic Treatment. Another promising, yet understudied, avenue involves the use of weight-loss medications after MBS. Emerging research suggests utility in weight-loss medications after MBS (13). The combination of Naltrexone and Bupropion (**NB**), also known as "Contrave," is an optimal starting point due to its consistent weight-loss evidence base, affordable costs, tolerable side-effects, safety profile, and putative mechanisms of action. In 2014, the FDA approved NB for obesity following empirical support from several RCTs performed with obesity (14). These RCTs reported significant clinically-meaningful weight losses with naltrexone plus sustained-release bupropion combined in fixed-dose pills. These

findings supporting NB medication are consistent with large RCTs which reported greater weight loss with NB than placebo (-6.5 vs -1.2% (14)). Although the name brand (Contrave) is expensive, the combination of Naltrexone and Bupropion are available at affordable prices. Putative mechanisms of action for NB seem relevant for post-MBS patients who might also be struggling with maladaptive eating behaviors, such as loss-of-control (LOC) eating. LOC eating and related eating-disorder psychopathology are consistent predictors of poor outcomes after MBS (15). As reviewed in the preliminary data section below, NB may be helpful in both reducing problematic eating such as LOC eating (i.e., binge eating) and weight loss. Putative mechanisms of action for NB is especially relevant for reducing LOC eating and weight per hypothesized effects on brain regions implicated in the regulation of food intake and weight based on the mechanisms of action of leptin (16).

Early Weight Loss. Meaningful early weight loss, ranging from 0.5 to 3% weight loss during the first 1-2 months of treatment, is a consistent predictor of weight loss by the end of treatment and longer-term (17). Earlier work has found that at least 1% weight loss early in treatment was associated with meaningful weight loss at the end of treatment (17).

Collectively, the lack of evidence-based treatments after MBS remains a critical and concerning gap in the field. An evidence base is urgently needed to direct the field in managing obesity after surgical intervention. Given that BWL and NB are both empirically-based weight-loss treatments, the proposed study will pilot the feasibility and acceptability of delivering behavioral treatment (BWL) to adults struggling with weight regain after MBS. Early weight loss responders will continue with BWL for the duration of treatment, while early non-responders will be given NB as an adjunct to BWL. The pilot will also examine whether augmenting behavioral treatment with NB results in weight loss and improvements in psychosocial functioning. These data will inform designs and provide effect size data to power larger definitive trials examining stepped care approaches with behavioral and pharmacological interventions for post-MBS.

3 - Rationale/Significance

3.1 Problem Statement

MBS is the most effective treatment for severe obesity and associated sequelae. Despite MBS' overall efficacy, weight regain with recurrence and/or onset of medical and psychological comorbidities is common and a matter of great concern. Very little is known about post-MBS treatments for weight regain.

3.2 Purpose of Study/Potential Impact

The goals of this proposal are to evaluate the feasibility and acceptability of evidence-based obesity treatments in post-MBS patients. All eligible subjects who experience weight regain after MBS will be given BWL. After one month of BWL treatment, "treatment response" will be determined based on early weight loss status because of its strong prognostic significance for optimal weight loss outcomes. Early weight-loss responders will continue BWL treatment, while *non*-responders will be given a pharmacologic agent to augment BWL treatment. This study aims to explore whether the addition of specific pharmacotherapy to BWL amongst initial non-responders improves outcomes. The study will compare the two treatment conditions and will examine within-group weight and psychosocial changes over time in the combined treatment condition; these data will serve as pilot data and represent effect-size estimates to design and power larger definitive treatment trials testing combined behavioral and pharmacological interventions and stepped-care approaches to prevent weight regain after MBS.

